6.2.2.6. Disease control

Disease Control (DC) is defined as BOR of CR, PR, non-CR/non-PD or SD. Both CR and PR must be confirmed by repeat assessments performed no less than 4 weeks after the criteria for response are first met. DC rate (DCR) is the proportion of patients with DC.

DCR will be summarized by frequency counts and percentages.

6.2.2.7. Duration of response

Duration of Response (DR) is defined, for patients with OR, as the time from the first documentation of objective response (CR or PR) to the date of first documentation of PD or death due to any cause. If a patient has not had an event (PD or death), DR is censored at the date of last adequate tumor assessment. The censoring rules for DR are as described for PFS in Table 9.

$$\text{DR (months)} = [\text{date of event or censoring} - \text{first date of OR} + 1] / 30.4375$$

Kaplan-Meier estimates (product-limit estimates) will be presented by treatment arm together with a summary of associated statistics including the median DR time with 2-sided 95% CIs. In particular, the DR rate at 3, 6, 9, 12, 18, 24, 30 months will be estimated with corresponding 2-sided 95% CIs. The CIs for the median will be calculated according to [Brookmeyer and Crowley](#) and the CIs for the survival function estimates at the time points defined above will be derived using the log-log transformation according to [Kalbfleisch and Prentice](#) (confype=loglog default option in SAS Proc LIFETEST) with back transformation to a CI on the untransformed scale. The estimate of the standard error will be computed using Greenwood's formula.

DR will be displayed graphically and analyzed using Kaplan-Meier methodology. If the number of patients with OR is small, the Kaplan-Meier method may not provide reliable estimates. In this case, only descriptive statistics or listings will be provided.

6.2.2.8. Time to response

Time to response (TTR) is defined, for patients with OR, as the time from the date of randomization to the first documentation of objective response (CR or PR) which is subsequently confirmed.

$$\text{TTR (in months)} = [\text{first date of OR} - \text{date of randomization} + 1] / 30.4375$$

TTR will be summarized using simple descriptive statistics (mean, SD, median, min, max, Q1, Q3).

6.2.2.9. Progression-free survival on next-line therapy (PFS2)

PFS2 is defined as the time from the date of randomization to discontinuation of next-line treatment after first objective disease progression by investigator assessment, second objective disease progression by investigator assessment after initiation of next-line treatment, or death from any cause, whichever occurs first.

$$\text{PFS2 (months)} = [\text{date of event or censoring} - \text{start date} + 1] / 30.4375$$

A patient will be considered to have an event if

- 1) the patient had objective PD on or prior to start of next-line anti-cancer treatment, AND started next-line anti-cancer treatment, AND (had objective PD after start of next-line anti-cancer treatment OR discontinued next-line anti-cancer treatment)

OR

- 2) the patient died.

Kaplan-Meier estimates (product-limit estimates) will be presented by treatment arm together with a summary of associated statistics including the median PFS2 time with 2-sided 95% CIs. In particular, the PFS2 rate at 6, 12, 18, 24, 30, 36, 48, 60 months will be estimated with corresponding 2-sided 95% CIs. The CIs for the median will be calculated according to [Brookmeyer and Crowley](#) and the CIs for the survival function estimates at the time points defined above will be derived using the log-log transformation according to [Kalbfleisch and Prentice](#) (conftype=loglog default option in SAS Proc LIFETEST) with back transformation to a CI on the untransformed scale. The estimate of the standard error will be computed using Greenwood's formula.

The censoring and event date options to be considered for PFS2, each corresponding censoring reason and its hierarchy are presented in Table 14. Frequency (number and percentage) of patients with an event (PD after next line treatment, discontinuation of next-line treatment or death) and censoring reasons will be presented by treatment arm.

Table 14. Outcome, Event Dates, Censoring Reasons and Hierarchy for PFS2 Analyses

Scenario	Date of event/ censoring	Event/ Censoring reason/ Censoring hierarchy
(No PD ^a) and (no death)	Date of last adequate tumor assessment ^b documenting no PD	Censored/ No PD/ 1
(No PD ^a) and death	Date of death	Event (Death)
(PD ^a date > NTX ^c start date) and (no death)	Start date of NTX ^c	Censored/ Start of new anti-cancer treatment before PD/ 2
(PD ^a date > NTX ^c start date) and death	Date of death	Event (Death)
(PD ^a date ≤ NTX ^c start date) and (PD2 ^d date > NTX ^c start date)		

 If PD2 date ≤ NTX^c end date 	Date of PD2	Event (PD after start of next line anti-cancer treatment)

 If PD2 date > NTX^c end date 	End date of NTX ^c	Event (Discontinuation of next line anti-cancer treatment)
(PD ^a date ≤ NTX ^c start date) and (no PD2 ^d) and (no death)		

 If NTX^c end date is non-missing 	End date of NTX ^c	Event (Discontinuation of next line anti-cancer treatment)

 Else if [withdrawal of consent date ≥ date of randomization OR End of study (EOS) = Subject refused further follow-up] 	(Withdrawal of consent date) or (EOS visit date where subject refusal of further follow-up is recorded)	Censored/ Withdrawal of consent/ 3

 Else if [lost to follow-up in any disposition page] 	Last contact date	Censored/ Lost to follow-up/ 4

 Else if no prior conditions are met 	Last contact date	Censored/ Ongoing without PFS2 event/ 5
(PD ^a and no NTX ^c) and (no death)	Last contact date	Censored/ Ongoing without PFS2 event/ 6
(PD ^a date ≤ NTX ^c start date) and (no PD2 ^d) and death		

 If NTX^c end date is non-missing 	End date of NTX ^c	Event (Discontinuation of next line anti-cancer treatment)

 Else if the prior condition is not met 	Date of death	Event (Death)

Scenario	Date of event/ censoring	Event/ Censoring reason/ Censoring hierarchy
(PD ^a and no NTX ^c) and death	Date of death	Event (Death)

^a PD is the first PD by investigator assessment per RECIST v1.1, without considering any censoring rules

^b If there are no adequate post-baseline assessments, then the censoring date is the date of randomization. If patient has initiated next-line anti-cancer treatment, the last adequate post-baseline assessment on or prior to start date of next-line anti-cancer treatment will be considered.

^c NTX is the next-line anti-cancer treatment.

^d PD2 is the first PD after initiation of next-line anti-cancer treatment by investigator assessment per RECIST v1.1, without considering any censoring rules.

The PFS2 time or censoring time and the reasons for censoring will also be presented in a patient listing.

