17. **Survival Assessment:** All patients will be followed for survival and subsequent anticancer therapies every 3 months ( $\pm 14$  days) until death, end of the study or patient withdrawal of consent, whichever comes first. Information will be collected by telephone call unless the patient is visiting the site for other reasons. The Sponsor will request an "ad hoc" survival update prior to each protocol-specified interim analysis and final analysis. The investigator or designee must make every effort to collect the patient's status through contacting the patient or a relative or their usual health care provider by telephone or other allowed methods. These contact attempts should be documented in the patient's medical record.
18. **Patient-Reported Outcome Questionnaire:** FKSI-19 and EUROQoL 5-Dimension (EQ-5D) are to be administered at the End of Treatment/Withdrawal visit. PROs should be administered prior to other End of Treatment/Withdrawal measures. Beyond End of Treatment (ie, follow-up period), PRO assessments will be collected at the same time a tumor assessment is performed.
19. **Pharmacokinetics:** In Arm A, PK blood samples for avelumab (3.5 mL) will be taken 1 month after end of avelumab treatment. Details are outlined in Section 7.3.
- [REDACTED]
21. **De Novo Tumor Biopsy:** A *de novo* (ie, fresh biopsy) tumor sample should also be collected at End of Treatment/Withdrawal visit, unless clinically contraindicated. Tumor tissue from cytologic sampling (eg, fine needle aspiration, including FFPE cell pellet material), is not adequate and should not be submitted. The *de novo* biopsy(ies) should be formalin-fixed and paraffin-embedded as per routine (see Study Manual), [REDACTED] should be submitted to the Central Laboratory. See [Section 7.5.1](#).
22. **Anti-Avelumab Antibodies (Anti-Drug Antibodies, ADAs) and Neutralizing Antibodies (Nab):** In Arm A, one blood sample (3.5 mL) for anti-avelumab antibodies (and simultaneous pharmacokinetic draws for measurement of avelumab) will be collected at 30 days after the end of avelumab treatment. All the samples that are positive for ADA may also undergo characterization for Nab. See [Section 7.4](#).
23. **MUGA Scan or ECHO.** For the evaluation of the left ventricular ejection fraction, the technique used at screening will be consistently used throughout the study, in the following assessments.

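### SAP Table 14 ends the PFS2 time at risk of patients who start next-line therapy before or without progression according to whether they later die

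*SAP*

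**What the plan says.** SAP 6.2.2.9 allows two routes to a PFS2 event. The first requires that "the patient had objective PD on or prior to start of next-line anti-cancer treatment, AND started next-line anti-cancer treatment", and then progressed again or stopped that treatment. The second is that "the patient died".

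Table 14 turns this into dates. Numbering its first four rows in order:

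- Row 1, "No PD ^a) and (no death": censored at the last adequate tumor assessment. Footnote b adds that, if next-line treatment was started, "the last adequate post-baseline assessment on or prior to start date of next-line anti-cancer treatment will be considered".
- Row 2, no progression and death: event at the death date.
- Row 3, "PD ^a date > NTX ^c start date) and (no death": censored at next-line start.
- Row 4, "PD ^a date > NTX ^c start date) and death": event at the death date.

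A later row, "PD ^a and no NTX ^c) and (no death", is censored at last contact. Protocol 9.3.2 and SAP 3.2.2 give a shorter definition (next-line discontinuation, second progression or death) that does not require progression before next-line therapy.

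**The concern.** Under route 1, a patient who starts next-line therapy before or without progression can no longer have a progression or discontinuation event. Only death remains, and vital status continues to be collected: "All patients will be followed for survival and subsequent anticancer therapies every 3 months". Rows 1 to 4 nevertheless end this patient's time at risk at two different points, and the choice between them depends on something learned only afterwards. Time after the switch enters the analysis if the patient later dies and is discarded if the patient survives. Kaplan-Meier estimation assumes that censoring carries no information about the later event; here it is determined by that event.

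PFS2 is a stated secondary objective, with medians and rates to 60 months reported by arm. At stake is how accurately those figures describe the endpoint that 6.2.2.9 defines.

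**Working it through.** The documents give no PFS2 event count, power or expected value, so there is no stated figure to reproduce.

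**Step 1: the rows side by side, for early switchers only.**

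| Status at cut-off | Alive | Dead |
|---|---|---|
| Progression after next-line start | censored at next-line start (row 3) | event at death (row 4) |
| No progression | censored at last adequate scan on or before next-line start (row 1, footnote b) | event at death (row 2) |

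**Step 2: direction.** The comparator keeps the 6.2.2.9 event rule and censors living early switchers at last contact. SAP 5.3.3.1 builds last contact from, among others, randomization, tumor assessment and later anti-cancer therapy dates. It is therefore never before the Table 14 censoring date: in row 3 the later progression scan itself counts, and in row 1 the censoring date is itself a scan date or randomization.

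The estimate is S(t) = product over event times u ≤ t of (1 − d_u/n_u). Both rules give the same events on the same dates, so every d_u is equal. Table 14 removes survivors no later than the comparator does, so its n_u is smaller or equal. Each factor is equal or lower, and so is S(t). In 5,000 random data sets with ties there was no violation, and Table 14 was strictly lower at some time in 4,400.

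**Step 3: a case to check by hand.** Ten patients: deaths at months 6, 12, 18 and 24; six survivors last seen at month 30, three of whom switched early at month 3.

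- Table 14: 6/7, then × 5/6, × 4/5, × 3/4, giving 0.857, 0.714, 0.571, 0.429.
- Last contact: 9/10, then × 8/9, × 7/8, × 6/7, giving 0.900, 0.800, 0.700, 0.600.

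**Step 4: illustrative size.**

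- From SAP 5.1.1 (PD-L1 positive, Arms A and B): PFS medians 16.9 and 11 months, used here as time to progression; OS medians 37.7 and 26.4 months; 21-month accrual, taken as uniform.
- From SAP Table 8: month 46, the projected third OS interim under the alternative.
- Assumed: exponential times; progression-to-death medians of 14.3 and 10.8 months, which reproduce the OS medians; next-line therapy starting 1 month after progression and ending with median 7 months; early switch at a uniform fraction of time to progression; median survival of 24 months after an early switch; half of living early switchers in row 1 and half in row 3; 300,000 simulated patients per arm.

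Each cell is Table 14 vs last contact:

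| Early switchers | Median A (months) | Median B (months) | 36-month rate A | 36-month rate B |
|---|---|---|---|---|
| 5% | 25.0 vs 25.4 | 18.4 vs 18.7 | 31.9% vs 33.1% | 17.2% vs 18.7% |
| 10% | 25.1 vs 25.9 | 18.5 vs 19.1 | 31.9% vs 34.3% | 17.1% vs 20.2% |
| 20% | 25.0 vs 26.7 | 18.8 vs 20.1 | 30.9% vs 35.8% | 16.6% vs 23.0% |
| 30% | 25.1 vs 27.9 | 19.0 vs 21.1 | 30.7% vs 38.1% | 16.3% vs 25.8% |

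At month 61 (projected final OS analysis), the median shift over the same shares is 0.3 to 1.8 months in Arm A and 0.2 to 1.3 in Arm B. I then varied survival after switching (12, 24, 36 months), next-line median (5, 7, 9 months), timing of the switch, row split, arm and cut-off: 216 settings per share. The median shift ran from 0.04 to 0.7 months at 5%, 0.1 to 1.4 at 10%, 0.2 to 2.9 at 20% and 0.3 to 4.5 at 30%.

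**The case against.** The strongest objection is that the direction depends on the comparator. Under the shorter definition in protocol 9.3.2 and SAP 3.2.2, an early switcher who stops next-line therapy or progresses on it has an event. Adding that curve to the month-46 model, with the same 7-month next-line median for early switchers, gives these medians in the order broader definition, Table 14, last contact. Arm A: 23.8, 25.0, 25.9 months at 10% and 21.5, 25.0, 27.7 at 30%. Arm B: 17.6, 18.5, 19.1 and 16.4, 19.1, 21.1. Here Table 14 lies above the broader-definition curve, and last-contact censoring moves further from it. This stands. A reader might infer that Table 14 understates PFS2 outright; the documents support that only relative to the 6.2.2.9 event rule.

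Relatedly, a patient who switches at month 3, progresses at month 6, stops next-line therapy at month 7 and is alive at month 40 would count as event-free for 40 months. That follows from the event rule in 6.2.2.9, not from the censoring date. It is a reason to show the broader definition as well, not to let vital status decide the censoring.

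Censoring at the last scan is usually defended because progression status is unknown afterwards. That holds for patients with no progression and no next-line therapy, whose row can stay as it is. It does not hold for early switchers, whose later progression cannot be an event.

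A reader might also infer that the affected patients are hidden. Row 1 does mix switchers and non-switchers under one reason. But the Table 10 censoring reasons, repeated for investigator-assessed PFS (SAP 6.2.2), report the start of new therapy by arm under a somewhat broader definition of therapy, and PFS2 censoring reasons are listed by patient. Most of the count can be recovered.

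Finally, the early-switch share is unknown, and parts of the protocol discourage early switching: expedited central review (7.8), treatment past progression (5.4.4), and continuation of one drug in Arm A (3.1.1). This limits the likely size but does not remove the defect.

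**Conclusion.** The point holds within the SAP's own event rule. For early switchers, Table 14 makes time at risk depend on later vital status, and each arm's PFS2 curve is equal to or below the curve with survivors censored at last contact. The direction follows from the risk sets and needs no assumption about switching rates. The size does: in the base model the median shift is 0.2 to 0.4 months at 5% early switchers over the two cut-offs, and larger shares give larger shifts.

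A reader might go further and infer a bias between arms, since the trial is open-label. The documents do not support this: the inequality applies within each arm, and nothing gives the early-switch share by arm. Nor is any test affected, because PFS2 is summarized descriptively with no alpha. No direction is claimed against the broader definition in protocol 9.3.2 and SAP 3.2.2. The rule should be corrected before PFS2 is reported, but it does not touch the primary conclusions.

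**What to change.** Make the time at risk of early switchers independent of later vital status:

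- Keep the 6.2.2.9 event rule. In row 3, censor at last contact.
- Split row 1. Living patients with no progression who started next-line therapy are censored at last contact, with their own censoring reason and hierarchy position; those with no next-line therapy stay as they are. Amend footnote b to match.
- Report the present Table 14 rule as a sensitivity analysis, with the number of early switchers by arm.
- State in the SAP that protocol 9.3.2 and SAP 3.2.2 differ in substance from 6.2.2.9. Do not rewrite them as an editorial change, because requiring prior progression alters who can have an event. Add a sensitivity analysis under the broader definition, counting next-line discontinuation or progression after next-line start for early switchers too. The protocol's schedule after the third interim stops scans at the start of new therapy, so later progressions will be incompletely captured there; say so in the report.

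The cost is one date cell, one row split, one footnote, two sensitivity analyses and a short note. Last-contact and next-line dates are already collected, so no new visits, scans or data are needed.

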6.2.3. Pharmacokinetic endpoints

The following pharmacokinetic analyses will be based on the PK analyses set.

C_{trough} for avelumab and C_{trough} and C_{max} axitinib will be summarized descriptively (n, mean, SD, CV, median, minimum, maximum, geometric mean, its associated CV, and 95% confidence interval) by cycle and day.

Dose normalized parameters (e.g., CDN- C_{max} , CDN- C_{trough}) will be reported as appropriate. The trough concentrations for avelumab and axitinib will be plotted for each dose (if axitinib is dose titrated) using a box whisker plot by cycle and day in order to assess the attainment of steady state.

Pharmacokinetic parameters for avelumab and axitinib will be taken from observed values or derived from plasma concentration-time data as described in Section 3.2.4.

Presentation of pharmacokinetic data will include:

- Descriptive statistics (n, mean, SD, %CV, median, minimum, maximum) of plasma concentrations will be presented in tabular form by dose level, cycle, day and nominal time. Additionally similar descriptive statistics will also be generated for dose-normalized axitinib pharmacokinetic parameters, if applicable.
- Pharmacokinetic parameters for avelumab and axitinib will be listed and summarized by cycle and study day using descriptive statistics (n, mean, SD, %CV, median, minimum, maximum, geometric mean and its associated %CV, and 95% CI). PK parameters with zero values will be excluded from the calculation of geometric means and its associated %CV. If an inpatient dose escalation or reduction occurs, dose-dependent PK parameters (C_{max}) for that patient may be dose-normalized when it is known that the drug exhibits linear PK within the dose range and other PK parameters will be reported as estimated; or may only be included in descriptive statistics and summary plots up to the time of the dose change. In addition, dose-normalized C_{max} parameters will be

summarized (as described above) using data in which different avelumab and axitinib doses were administered.

- Box plots for C_{\max} and C_{trough} for axitinib will be generated. Individual data points, the geometric mean and the median of the parameter in each treatment will be overlaid on the box plots. If a treatment arm has limited evaluable PK data ($n < 4$), matchstick plots showing changes in C_{\max} and C_{trough} for each drug in individual patients will then be generated. The geometric mean of the parameter in each treatment will be overlaid in the plots. In addition, box plots for dose-normalized axitinib C_{\max} and C_{trough} parameters will be created using data from patients in Arm A.
- C_{trough} for avelumab will be plotted for each treatment arm using a box-whisker plot by cycle and day within cycle in order to assess the attainment of steady-state.

6.2.4. Population pharmacokinetic endpoints

Pharmacokinetic and pharmacodynamic data from this study may be analyzed using modeling approaches and may also be pooled with data from other studies to investigate any association between avelumab and axitinib exposure and biomarkers or significant safety/efficacy endpoints. The results of these analyses, if performed, may be reported separately.

6.2.5. Biomarker endpoints

Biomarkers will be summarized at all timepoints described below:

- Soluble proteins: screening, C1D1, C2D1, C3D1 and EOT.
- Tumor based biomarkers, archival FFPE Tumor Tissue Block: screening
- Tumor based biomarkers, de novo Tumor Biopsy: screening and EOT.

Summary statistics, using descriptive statistics (mean, SD, median, Q1, Q3, minimum, and maximum), at each timepoint and percent change from the value at screening if available (for continuous markers) will be provided separately for each treatment arm.

For each defined biomarker or group thereof (signature), patients may be classified as positive, negative, or unknown according to scoring algorithms and cutoffs established external to this study. Subset analyses for PFS by BICR assessment and OS will be performed for the subgroups defined by these cutoffs using the methodology described in Section 6.4. If there are fewer than 20 events in a subgroup for PFS by BICR assessment or OS, only descriptive summaries will be produced.

6.2.6. Endpoints for immunogenicity data of avelumab

All analyses described below are performed for Arm A only.

Blood samples for avelumab immunogenicity testing will be collected within 2 hours before the start of the avelumab infusion on Day 1, Day 15 and Day 29 of Cycle 1, on Day 1 and Day 29 of Cycles 2-4, on Day 1 of Cycle 6, and then every 2 cycles thereafter. An additional sample must be collected at 30 days after the last dose of avelumab.

Samples positive for ADA will be analyzed for titer and may be analyzed for nAb. As of the finalization of this SAP, the nAb assay is not yet available, therefore the analyses of nAb data described in the following sections will only be conducted contingent upon assay and data availability at the time of reporting.

Patients will be characterized into different ADA categories based on the criteria defined in Table 15.

Table 15 Patients Characterized Based on Anti-Drug Antibody Results (ADA Status)

Category	Definition	Subjects at Risk (Denominator for Incidence)
ADA never-positive	No positive ADA results at any time point; ADA-negative patients (titer < cutpoint)	Number of patients with at least one valid ADA result at any time point
ADA ever-positive	At least one positive ADA result at any time point; ADA-positive patients (titer ≥ cutpoint)	Number of patients with at least one valid ADA result at any time point
Baseline ADA positive	A positive ADA result at baseline	Number of patients with valid baseline ADA result
Treatment-boosted ADA	A positive ADA result at baseline and the titer ≥ 8×baseline titer at least once after treatment with avelumab	Number of patients with valid baseline ADA results and at least one valid post-baseline ADA result
Treatment-induced ADA	Patient is ADA-negative at baseline and has at least one positive post-baseline ADA result; or if patient does not have a baseline sample, the patient has at least one positive past-baseline ADA result	Number of patients with at least one valid post-baseline ADA result and without positive baseline ADA result (including missing, NR)
Transient ADA response	If patients with treatment-induced ADA have (a single positive ADA result or duration between first and last positive result <16 weeks) and ADA result at the last assessment is not positive.	Number of patients with at least one valid post-baseline ADA result and without positive baseline ADA result (including missing, NR)
Persistent ADA response	If patients with treatment-induced ADA have duration between first and last positive ADA result ≥16 weeks or a positive ADA result at the last assessment	Number of patients with at least one valid post-baseline ADA result and without positive baseline ADA result (including missing, NR)

ADA: anti-drug antibody, NR = not reportable.

Patients will be characterized into different nAb categories based on the criteria in Table 16. For nAb, treatment-boosted is not applicable since no titer result is available.

Table 16 Patients Characterized Based on Neutralizing Antibody Results (nAb Status)

Category	Definition	Subjects at Risk (Denominator for Incidence)
nAb never-positive	No positive nAb results at any time point	Number of patients with at least one valid ADA result at any time point
nAb ever-positive	At least one positive nAb result at any time point	Number of patients with at least one valid ADA result at any time point
Baseline nAb positive	A positive nAb result at baseline	Number of patients with valid baseline ADA result
Treatment-induced nAb	Patient is not nAb positive at baseline and has at least one positive post-baseline nAb result; or if patient does not have a baseline sample, the patient has at least one positive post-baseline ADA result	Number of patients with at least one valid post-baseline ADA result and without positive baseline nAb result (including missing, NR)
Transient nAb response	If patients with treatment-induced nAb have (a single positive nAb result or duration between first and last positive result <16 weeks) and nAb result at the last assessment is not positive.	Number of patients with at least one ADA valid post-baseline result and without positive baseline nAb result (including missing, NR)
Persistent nAb response	If patients with treatment-induced nAb have duration between first and last positive nAb result ≥16 weeks or a positive nAb result at the last assessment	Number of patients with at least one valid post-baseline ADA result and without positive baseline nAb result (including missing, NR)

ADA = antidrug antibody, nAb = neutralizing antibody, NR = no result.

The number and percentage of patients in each ADA and nAb category will be summarized.

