## **7.4. Immunogenicity Assessment**

A total of 3.5 mL of whole blood will be collected into a SST at the designated times to provide serum for evaluation of avelumab immunogenicity. Immunogenicity blood samples will be assayed for anti-avelumab antibodies using a validated analytical method. All of the samples that are positive for ADA may also undergo characterization for neutralizing antibodies. Additional details regarding the collection, processing, storage, and shipping of the blood samples will be provided in the Study Manual.

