6.2.6.3. Analysis of PK, safety and efficacy by immunogenicity status

The following ADA and nAb status will be used for the analyses described below.

ADA

- ADA ever-positive versus ADA never-positive
- ADA: treatment-induced ADA versus ADA never-positive or baseline ADA positive

nAb

- nAb ever-positive versus nAb never-positive
- nAb: treatment-induced nAb versus nAb never-positive or baseline nAb positive

Data listings will include immunogenicity data together with relevant PK, safety and efficacy data.

PK parameters and immunogenicity status

The following analyses will include patients in both the immunogenicity analysis set and in the PK parameter analysis set. The PK endpoint pertinent to the immunogenicity analyses is C_{trough} .

Blood samples for avelumab PK will be collected pre-dose on Day 1, Day 15 and Day 29 of Cycle 1, on Day 1 and Day 29 of Cycles 2-4, Day 1 of Cycle 6, every 2 cycles after Cycle 6, and 1 month after end of avelumab treatment.

C_{trough} will be summarized descriptively (n, mean, SD, CV, median, minimum, maximum, geometric mean, its associated CV, and 95% CI) by nominal time and ADA status. Linear-linear and log-linear plots of mean and median for C_{trough} over nominal time and by ADA status will be presented.

Among patients with treatment-induced ADA, analyses will be conducted to assess whether C_{trough} has any changes before and after the first positive ADA assessment. To be included in this analysis, patients must have the same PK parameter available both before and after the first positive ADA assessment. Relative PK day will be calculated as:

$$(\text{PK assessment nominal day}) - (\text{first positive ADA assessment nominal day}).$$

Nominal day is the protocol scheduled timing for an assessment. For example, if C_{trough} is collected on Day 1 of Cycle 2 and the first positive ADA result is observed on Day 1 of Cycle 3, then the relative PK day for this C_{trough} is -42. Linear-linear and log-linear plots of mean and median for C_{trough} over relative PK day will be presented.

As data permit, the analyses described above will be repeated for nAb.

Safety and immunogenicity status

The following analyses will include patients in the immunogenicity analysis set.

The frequency (number and percentage) of patients with each of the following will be presented by ADA status.

- TEAEs, by SOC and PT
- TEAEs leading to dose reduction of avelumab, by SOC and PT

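### If any ADA-positive samples go untested for neutralizing antibodies, SAP Table 16 counts those patients as nAb never-positive, because it has no 'not determined' category

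*SAP*

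**What the plan says.** All of this concerns Arm A only.

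- **Testing rule.** SAP 6.2.6: "Samples positive for ADA will be analyzed for titer and may be analyzed for nAb". Protocol 7.4: "All of the samples that are positive for ADA may also undergo characterization for neutralizing antibodies". Titer is mandatory in the SAP; nAb is not.
- **Assay status.** SAP 6.2.6 records that no nAb assay existed when the SAP was finalised, and says the nAb analyses "will only be conducted contingent upon assay and data availability at the time of reporting".
- **Categories (SAP Table 16).** Never-positive is "No positive nAb results at any time point"; ever-positive is "At least one positive nAb result at any time point". The denominator for both is "Number of patients with at least one valid ADA result at any time point". The baseline-positive row uses patients with a valid baseline ADA result. No row covers patients who were untested or whose status is unknown.
- **Treatment-induced row.** A patient with no baseline sample qualifies on a positive post-baseline ADA result, not a nAb result.
- **Use.** "The number and percentage of patients in each ADA and nAb category will be summarized". SAP 6.2.6.3 then compares "nAb ever-positive versus nAb never-positive" for avelumab trough concentration and for safety, as far as the data allow. Protocol 9.3.2 commits to reporting the percentage of patients with neutralizing antibodies.

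**The concern.** Testing is sequential: ADA first, then nAb on ADA-positive samples. Calling an ADA-negative patient nAb-negative is therefore reasonable. The gap is the ADA-positive patient whose positive samples were never run in the nAb assay, or whose results are pending at the cut-off. That patient has no positive nAb result and so meets the never-positive definition. A valid ADA result keeps the patient in the denominator, and without a test the patient cannot enter the ever-positive numerator. Missing is scored as negative.

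Two outputs are exposed: the reported nAb incidence, which belongs to a secondary immunogenicity endpoint, and the never-positive reference group in 6.2.6.3. Other parts of the SAP handle this differently. Table 15 bases each ADA category on valid results of the ADA test itself, and SAP 6.2.5 allows biomarker status to be unknown.

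**Working it through.** The plan states no ADA or nAb rate, so there is no figure to reproduce. The classification error follows from the text; its size can only be illustrated.

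**Inputs**
- N = 415 in Arm A (830 planned, randomized 1:1; SAP 2.2).
- a = 15% ADA ever-positive, q = 50% of those truly nAb-positive, u = 25% or 50% of ADA-positive patients untested. All three are assumptions; a range follows.
- Testing is taken to be unrelated to nAb status.

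**Formulas**
- True incidence = a·q = 0.15 × 0.50 = 7.5%.
- Table 16 incidence = a·q·(1 − u), so the relative understatement is u.
- Untested patients scored never-positive = N·a·u, where N·a = 62.25.
- Truly positive share of the never-positive group = N·a·q·u / [N − N·a·q·(1 − u)].
- Bounds, with undetermined patients counted all negative or all positive: a·q·(1 − u) to a·q·(1 − u) + a·u.

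| | u = 25% | u = 50% |
|---|---|---|
| True incidence | 7.5% | 7.5% |
| Table 16 incidence | 5.6% | 3.8% |
| Untested, scored never-positive | 15.6 (about 16) | 31.1 (about 31) |
| Truly nAb-positive among never-positive | 7.8/391.7 = 2.0% | 15.6/399.4 = 3.9% |
| Untested dropped from denominator only | 23.3/399.4 = 5.8% | 15.6/383.9 = 4.1% |
| nAb-positive among tested ADA-positive | 23.3/46.7 = 50% | 15.6/31.1 = 50% |
| Bounds on incidence | 5.6% to 9.4% | 3.8% to 11.3% |

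If a share c of the reference group is truly nAb-positive, an observed difference in means is (1 − c) times the true one. The 6.2.6.3 comparison therefore shrinks by about 2% to 4%.

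**Range over other assumed rates**

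| a | q | u | True | Table 16 | Bounds |
|---|---|---|---|---|---|
| 5% | 30% | 25% | 1.5% | 1.1% | 1.1% to 2.4% |
| 10% | 60% | 25% | 6.0% | 4.5% | 4.5% to 7.0% |
| 10% | 60% | 50% | 6.0% | 3.0% | 3.0% to 8.0% |
| 20% | 60% | 50% | 12.0% | 6.0% | 6.0% to 16.0% |

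At u = 0 the Table 16 incidence equals the true one in every case.

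**Treatment-induced row.** Suppose 10% of patients lack a baseline sample, all positivity arises after baseline, and testing is complete. With a = 15% and q = 50%, the row gives 0.9 × 7.5% + 0.1 × 15% = 8.25% against a true 7.5%. With a = 10% and q = 60%, it gives 0.9 × 6.0% + 0.1 × 10% = 6.4% against 6.0%. The ADA wording pushes this row upward, and that does not depend on any sample going untested.

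**The case against.** The strongest reply is that partial testing is not planned. The optional wording in SAP 6.2.6 is followed directly by the explanation that no assay existed yet. Protocol 7.4 refers to all ADA-positive samples. Protocol 9.3.2 says the neutralizing-antibody percentage will be reported. A fair reading is all-or-none: either the assay becomes available and every ADA-positive sample is run, or no nAb analysis is done. The availability condition, and the proviso in 6.2.6.3 that nAb analyses are repeated only as data permit, also leave room to withhold results from incomplete data.

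Part of this stands. A reader might infer from the optional wording that a subset will be tested and that the reported incidence will therefore be too low. The documents do not support that: nothing in them schedules subset testing, and complete testing removes the error. A reader might also infer serious damage to the exposure comparison. About half of the 16 or 31 misplaced patients are, by assumption, truly nAb-negative and belong in the reference group, so the shrinkage is small.

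What does not stand is that the provisos close the gap. They decide whether an analysis is run, not how an untested ADA-positive patient is classified once it is, and neither makes complete testing a condition. With the assay unavailable when the SAP was written, results still pending at a cut-off are a foreseeable case.

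**Conclusion.** The point holds conditionally. If any ADA-positive patients are untested, Table 16 labels them never-positive and keeps them in the denominator. The ever-positive and baseline-positive rates are then understated in relative terms by the untested share, assuming testing is unrelated to nAb status. Under the assumed 15% and 50%, that means 5.6% or 3.8% instead of 7.5% with 25% or 50% untested; none of these rates is in the documents. Contamination of the 6.2.6.3 reference group is minor, at about 2% to 4%.

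The direction is not the same in every row. The treatment-induced row has a separate upward pull from its ADA wording, so it would be wrong to infer that all nAb rates in the table are too low.

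This is a cheap clarification to a descriptive Arm A endpoint. No primary analysis, hypothesis test or ADA category is affected.

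**What to change.** - Define nAb never-positive as: all valid ADA results negative, or every ADA-positive sample tested and nAb-negative.
- Add a row for ADA-positive patients with nAb not determined: at least one ADA-positive sample untested and no positive nAb result. Exclude these patients from the nAb comparisons in 6.2.6.3.
- Do not rely on removing them from the denominator. That moves the illustrated incidence only from 5.6% to 5.8%, or from 3.8% to 4.1%, against a true 7.5%.
- Report instead nAb positivity among tested ADA-positive patients, and overall incidence with bounds that count undetermined patients as all negative and as all positive.
- In the treatment-induced row, require a positive post-baseline nAb result for patients without a baseline sample.

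The cost is revised table wording, one extra row and a few summary lines. No new data are collected, and with complete testing the extra row is empty.
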